Annex 4.

Coding of Malignancies

Table A4-1. Morphology Codes for the Definition of Non-melanoma Skin Cancers (Topography Code C44)

Description	ICD-O-3 codes
SQUAMOUS CELL NEOPLASMS	
Papillary carcinoma, in situ	M 8050/2
Papillary carcinoma, NOS	M 8050/3
Verrucous carcinoma, NOS	M 8051/3
Condylomatous carcinoma	"
Verrucous squamous cell carcinoma	"
Verrucous epidermoid carcinoma	"
Warty carcinoma	"
Papillary squamous cell carcinoma, noninvasive	M 8052/2
Papillary squamous cell carcinoma	M 8052/3
Papillary epidermoid carcinoma	"
Squamous cell carcinoma in situ, NOS	M 8070/2
Epidermoid carcinoma in situ, NOS	"
Intraepidermal carcinoma, NOS	"
Intraepithelial squamous cell carcinoma	"
Squamous cell carcinoma, NOS	M 8070/3
Epidermoid carcinoma, NOS	"
Squamous carcinoma	"
Squamous cell epithelioma	"
Squamous cell carcinoma, keratinizing, NOS	M 8071/3
Squamous cell carcinoma, large cell, keratinizing	"
Epidermoid carcinoma, keratinizing	"
Squamous cell carcinoma, large cell, nonkeratinizing, NOS	M 8072/3
Squamous cell carcinoma, large cell, nonkeratinizing, NOS	"
Epidermoid carcinoma, large cell, nonkeratinizing	"
Squamous cell carcinoma, small cell, nonkeratinizing	M 8073/3
Epidermoid carcinoma, small cell, nonkeratinizing	"
Squamous cell carcinoma, spindle cell	M 8074/3
Epidermoid carcinoma, spindle cell	"
Squamous cell carcinoma, sarcomatoid	"
Squamous cell carcinoma, adenoid	M 8075/3
Squamous cell carcinoma, pseudoglandular	"
Squamous cell carcinoma, acantholytic	"
Squamous cell carcinoma in situ with questionable stroma invasion	M 8076/2
Epidermoid carcinoma in situ with questionable stroma invasion	"
Squamous cell carcinoma, microinvasive	M 8076/3

Description	ICD-O-3 codes
Squamous cell carcinoma, with horn formation	M 8078/3
Bowen's disease	M 8081/2
Intraepidermal squamous cell carcinoma, Bowen type	"
Basaloid squamous cell carcinoma	M 8083/3
Squamous cell carcinoma 'clear cell type'	M 8084/3
BASAL CELL NEOPLASMS	
Basal cell carcinoma, NOS	M 8090/3
Basal cell epithelioma	"
Rodent ulcer	"
Pigmented basal cell carcinoma	"
Multifocal superficial basal cell carcinoma	M 8091/3
Multicentric basal cell carcinoma	"
Infiltrating basal cell carcinoma, NOS	M 8092/3
Infiltrating basal cell carcinoma, nonsclerosing	"
Infiltrating basal cell carcinoma, sclerosing	"
Basal cell carcinoma, morpheic	"
Basal cell carcinoma, desmoplastic type	"
Basal cell carcinoma, fibroepithelial	M 8093/3
Fibroepithelioma of Pinkus type	"
Fibroepithelial basal cell carcinoma, Pinkus type	"
Pinkus tumor	"
Fibroepithelioma, NOS	"
Basosquamous carcinoma	M 8094/3
Mixed basal-squamous cell carcinoma	"
Metatypical carcinoma	M 8095/3
Basal cell carcinoma, nodular	M 8097/3
Basal cell carcinoma, micronodular	"
Trichilemmal carcinoma	M 8102/3
Trichilemmal carcinoma	"
Pilomatrix carcinoma	M 8110/3
Pilomatrixoma, malignant	"
Pilomatricoma, malignant	"
Matrical carcinoma	"
Merkel cell carcinoma	M 8247/3
Merkel cell tumor	"
Primary cutaneous neuroendocrine carcinoma	"

Description	ICD-O-3 codes
ADNEXAL AND SKIN APPENDAGE NEOPLASMS	
Skin appendage carcinoma	M 8390/3
Adnexal carcinoma	"
Sweat gland adenocarcinoma	M 8400/3
Sweat gland carcinoma	"
Sweat gland tumor, malignant	"
Apocrine adenocarcinoma	M 8401/3
Nodular hidradenoma, malignant	M 8402/3
Hidradenocarcinoma	"
Malignant eccrine spiradenoma	M 8403/3
Sclerosing sweat duct carcinoma	M 8407/3
Syringomatous carcinoma	"
Microcystic adnexal carcinoma	"
Eccrine papillary adenocarcinoma	M 8408/3
Digital papillary adenocarcinoma	"
Eccrine poroma, malignant	M 8409/3
Porocarcinoma	"
Sebaceous adenocarcinoma	M 8410/3
Sebaceous carcinoma	"
Eccrine adenocarcinoma	M 8413/3
Ceruminous adenocarcinoma	M 8420/3
Ceruminous carcinoma	"

NOS = not otherwise specified.

Source: International Classification of Diseases for Oncology- Third Edition (ICD-O-3)

Table A4-2. Morphology Codes for the Definition of Skin Melanoma (Topography Code C44)

Cancer Description	ICD-O-3 codes
Melanoma in situ	M 8720/2
Malignant melanoma, NOS (except juvenile melanoma M-8770/0)	M 8720/3
Nodular melanoma	M 8721/3
Balloon cell melanoma	M 8722/3
Malignant melanoma, regressing	M 8723/3
Amelanotic melanoma	M 8730/3
Malignant melanoma in junctional naevus	M 8740/3
Malignant melanoma in precancerous melanosis	M 8741/3
Lentigo maligna	M 8742/2
Hutchinson melanotic freckle, NOS	"
Lentigo maligna melanoma	M 8742/3
Malignant melanoma in Hutchinson melanotic freckle	"
Superficial spreading melanoma	M 8743/3
Acral lentiginous melanoma, malignant	M 8744/3
Desmoplastic melanoma, malignant	M 8745/3
Neurotropic melanoma, malignant	"
Desmoplastic melanoma, amelanotic	"
Mucosal lentiginous melanoma	M 8746/3
Malignant melanoma in giant pigmented nevus	M 8761/3
Malignant melanoma in congenital melanocytic nevus	"
Mixed epithelioid and spindle cell melanoma	M 8770/3
Epithelioid cell melanoma	M 8771/3
Spindle cell melanoma, NOS	M 8772/3
Blue nevus, malignant	M 8780/3

NOS = not otherwise specified.

Source: International Classification of Diseases for Oncology- Third Edition (ICD-O-3)

Table A4-3. Morphology Codes for the Definition of Cutaneous Lymphomas With Primary Cutaneous Manifestations

Cancer Description	ICD-O-3 codes
Mature T-cell and Natural Killer Cell Lymphomas	970-971
Mycosis fungoides	M 9700/3
Pagetoid reticulosis	"
Sézary's syndrome	M 9701/3
Angioimmunoblastic T-cell lymphoma	M 9705/3
Peripheral T-cell lymphoma AILD	"
Angioimmunoblastic lymphoma	"
Subcutaneous panniculitis-like T-cell lymphoma	M 9708/3
Cutaneous T-cell lymphoma, NOS	M 9709/3
Cutaneous lymphoma, NOS	"
Anaplastic large cell lymphoma, T cell and Null cell type	M 9714/3
Large cell (Ki-1+) lymphoma	"
Anaplastic large cell lymphoma, NOS	"
Anaplastic large cell lymphoma, CD30+	"
Primary cutaneous CD30+ T-cell lymphoproliferative disorder	M 9718/3
Lymphomatoid papulosis	"
Primary cutaneous anaplastic large cell lymphoma	"
Primary cutaneous CD30+ large T-cell lymphoma	"
NK/T-cell lymphoma, nasal and nasal type	M 9719/3
T/NK-cell lymphoma	"
Angiocentric T-cell lymphoma	"
Malignant reticulosis, NOS	"
Polymorphic reticulosis	"

AILD = angioimmunoblastic lymphadenopathy-type T-cell lymphoma; NOS = not otherwise specified.

Source: International Classification of Diseases for Oncology- Third Edition (ICD-O-3)

Table A4-4. Morphology Codes for the Definition of Hodgkin and Non-Hodgkin Lymphomas

Cancer Description	ICD-O-3 codes
HODGKIN LYMPHOMA	M 965-966
Hodgkin lymphoma, NOS	M 9650/3
Hodgkin disease, NOS	"
Malignant lymphoma, Hodgkin	"
Hodgkin lymphoma, lymphocyte-rich	M 9651/3
Classical Hodgkin lymphoma, lymphocyte-rich	"
Hodgkin disease, lymphocyte predominance, NOS	"
Hodgkin disease, lymphocytic-histiocytic predominance	"
Hodgkin disease, lymphocyte predominance, diffuse	"
Hodgkin lymphoma, mixed cellularity, NOS	M 9652/3
Classical Hodgkin lymphoma, mixed cellularity, NOS	"
Hodgkin lymphoma, lymphocyte depletion, NOS	M 9653/3
Classical Hodgkin lymphoma, lymphocyte depletion, NOS	"
Hodgkin lymphoma, lymphocyte depletion, diffuse fibrosis	M 9654/3
Classical Hodgkin lymphoma, lymphocyte depletion, diffuse fibrosis	"
Hodgkin lymphoma, lymphocyte depletion, reticular	M 9655/3
Classical Hodgkin lymphoma, lymphocyte depletion, reticular	"
Hodgkin lymphoma, nodular lymphocyte predominance	M 9659/3
Hodgkin lymphoma, lymphocyte predominance, nodular	"
Hodgkin paragranuloma, NOS	"
Hodgkin paragranuloma, nodular	"
Hodgkin granuloma	M 9661/3
Hodgkin sarcoma	M 9662/3
Hodgkin lymphoma, nodular sclerosis, NOS	M 9663/3
Classical Hodgkin lymphoma, nodular sclerosis, NOS	"
Hodgkin disease, nodular sclerosis, NOS	"
Hodgkin lymphoma, nodular sclerosis, cellular phase	M 9664/3
Classical Hodgkin lymphoma, nodular sclerosis, cellular phase	"
Hodgkin lymphoma, nodular sclerosis, grade 1	M 9665/3
Classical Hodgkin lymphoma, nodular sclerosis, grade 1	"
Hodgkin disease, nodular sclerosis, lymphocyte predominance	"
Hodgkin disease, nodular sclerosis, mixed cellularity	"

Cancer Description	ICD-O-3 codes
Hodgkin lymphoma, nodular sclerosis, grade 2	M 9667/3
Classical Hodgkin lymphoma, nodular sclerosis, grade 2	"
Hodgkin disease, nodular sclerosis, lymphocyte depletion	"
Hodgkin disease, nodular sclerosis, syncytial variant	"
NON-HODGKIN LYMPHOMAS	M 967-972
Mature B-cell Lymphomas	M967-969
Malignant lymphoma, small B lymphocytic, NOS	M 9670/3
Malignant lymphoma, small lymphocytic, NOS	"
Malignant lymphoma, lymphocytic, well differentiated diffuse	"
Malignant lymphoma, lymphocytic, NOS	"
Malignant lymphoma, lymphocytic, diffuse, NOS	"
Malignant lymphoma, small cell, NOS	"
Malignant lymphoma, small lymphocytic, diffuse	"
Malignant lymphoma small cell diffuse	"
Malignant lymphoma, lymphoplasmacytic	M 9671/3
Malignant lymphoma, lymphoplasmacytoid	"
Immunocytoma	"
Malignant lymphoma, plasmacytoid	"
Plasmacytic lymphoma	"
Mantle cell lymphoma	M 9673/3
Mantle zone lymphoma	"
Malignant lymphoma, lymphocytic intermediate differentiation, diffuse	"
Malignant lymphoma, centrocytic	"
Malignant lymphomatous polyposis	"
Malignant lymphoma, mixed small and large cell, diffuse	M 9675/3
Malignant lymphoma, mixed lymphocytic-histiocytic, diffuse	"
Malignant lymphoma, mixed cell type, diffuse	"
Malignant lymphoma, centroblastic-centrolytic	"
Malignant lymphoma, centroblastic-centrolytic, diffuse	"
Primary effusion lymphoma	M 9678/3
Mediastinal large B-cell lymphoma	M 9679/3
Thymic large B-cell lymphoma	"
Malignant lymphoma, large B-cell, diffuse, NOS	M 9680/3
Diffuse large B-cell lymphoma, NOS	"
Malignant lymphoma, large cell, NOS	"
Malignant lymphoma, large B-cell, NOS	"
Malignant lymphoma, histiocytic, NOS	"

Cancer Description	ICD-O-3 codes
Malignant lymphoma, histiocytic, diffuse	"
Malignant lymphoma, large cell, cleaved and noncleaved	"
Malignant lymphoma, large cell, diffuse, NOS	"
Malignant lymphoma, large cleaved cell, NOS	"
Malignant lymphoma, large cell, cleaved, diffuse	"
Malignant lymphoma, large cell, cleaved, NOS	"
Malignant lymphoma, large cell, noncleaved, diffuse	"
Malignant lymphoma, large cell noncleaved, NOS	"
Malignant lymphoma, noncleaved, diffuse, NOS	"
Malignant lymphoma, noncleaved, NOS	"
Malignant lymphoma, large B-cell, diffuse, centroblastic, NOS	"
Malignant lymphoma, centroblastic, NOS	"
Malignant lymphoma, centroblastic, diffuse	"
Intravascular large B-cell lymphoma	"
Intravascular B-cell lymphoma	"
Angioendotheliomatosis	"
Angiotropic lymphoma	"
T-cell rich large B-cell lymphoma	"
Histiocyte-rich large B-cell lymphoma	"
T-cell rich/histiocyte-rich large B-cell lymphoma	"
Anaplastic large B-cell lymphoma	"
Malignant lymphoma, large B-cell diffuse, immunoblastic, NOS	M 9684/3
Malignant lymphoma, immunoblastic, NOS	"
Immunoblastic sarcoma	"
Malignant lymphoma, large cell, immunoblastic	"
Plasmablastic lymphoma	"
Burkitt lymphoma, NOS	M 9687/3
Burkitt tumor	"
Malignant lymphoma, undifferentiated, Burkitt type	"
Malignant lymphoma, small noncleaved, Burkitt type	"
Burkitt like lymphoma	"
Splenic marginal zone B-cell lymphoma	M 9689/3
Splenic marginal zone lymphoma, NOS	"
Splenic lymphoma with villous lymphocytes	"
Follicular lymphoma, NOS	M 9690/3
Malignant lymphoma, follicular, NOS	"
Malignant lymphoma, follicle center, follicular	"
Malignant lymphoma, follicle center, NOS	"

Cancer Description	ICD-O-3 codes
Malignant lymphoma, centroblastic-centrocytic, follicular	"
Malignant lymphoma, nodular, NOS	"
Malignant lymphoma, lymphocytic, nodular, NOS	"
Follicular lymphoma, grade 2	M 9691/3
Malignant lymphoma, mixed small cleaved and large cell, follicular	"
Malignant lymphoma, mixed lymphocytic-histiocytic, nodular	"
Malignant lymphoma, mixed cell type, follicular	"
Malignant lymphoma, mixed cell type, nodular	"
Follicular lymphoma, grade 1	M 9695/3
Malignant lymphoma, small cleaved cell, follicular	"
Follicular lymphoma, small cleaved cell	"
Malignant lymphoma, lymphocytic, poorly differentiated, nodular	"
Follicular lymphoma, grade 3	M 9698/3
Malignant lymphoma, large cell, follicular, NOS	"
Malignant lymphoma, large cell, noncleaved, follicular	"
Malignant lymphoma, histiocytic, nodular	"
Malignant lymphoma, noncleaved cell, follicular, NOS	"
Malignant lymphoma, large cleaved cell, follicular	"
Malignant lymphoma, centroblastic, follicular	"
Malignant lymphoma, lymphocytic, well differentiated, nodular	"
Marginal zone B-cell lymphoma NOS	M 9699/3
Marginal zone lymphoma, NOS	"
Mucosal-associated lymphoid tissue (MALT) lymphoma	"
MALT lymphoma	"
Bronchial-associated lymphoid tissue (BALT) lymphoma	"
BALT lymphoma	"
Skin-associated lymphoid tissue (SALT) lymphoma	"
SALT lymphoma	"
Monocytoid B-cell lymphoma	"
Nodal marginal zone lymphoma	"
MATURE T AND NK-CELL LYMPHOMAS	M970-971
Mature T-cell lymphoma, NOS	M 9702/3
Peripheral T-cell lymphoma, NOS	"
T-cell lymphoma, NOS	"
Peripheral T-cell lymphoma, pleomorphic small cell	"
Peripheral T-cell lymphoma, pleomorphic medium and large cell	"
Peripheral T-cell lymphoma, large cell	"

Cancer Description	ICD-O-3 codes
T-zone lymphoma	"
Lymphoepithelioid lymphoma	"
Lennert lymphoma	"
Hepatosplenic γ/δ (gamma-delta) cell lymphoma	M 9716/3
Intestinal T-cell lymphoma	M 9717/3
Enteropathy type intestinal T-cell lymphoma	"
Enteropathy associated T-cell lymphoma	"
PRECURSOR CELL LYMPHOBLASTIC LYMPHOMA	972
Precursor cell lymphoblastic lymphoma, NOS	M 9727/3
Malignant lymphoma, lymphoblastic, NOS	"
Malignant lymphoma, convoluted cell	"
Lymphoblastoma	"
Precursor B-cell lymphoblastic lymphoma	M 9728/3
Precursor T-cell lymphoblastic lymphoma	M 9729/3
MALIGNANT LYMPHOMAS, NOS OR DIFFUSE	M959
Malignant lymphoma, NOS	M 9590/3
Lymphoma, NOS	"
Microglioma	"
Malignant lymphoma, non-Hodgkin, NOS	M 9591/3
Non-Hodgkin lymphoma, NOS	"
B-cell lymphoma, NOS	"
Malignant lymphoma, noncleaved cell, NOS	"
Malignant lymphoma diffuse, NOS	"
Malignant lymphoma, lymphocytic, intermediate differentiation, nodular	"
Malignant lymphoma, small cell, noncleaved, diffuse	"
Malignant lymphoma, undifferentiated cell, non-Burkitt	"
Malignant lymphoma, undifferentiated cell type, NOS	"
Lymphosarcoma, NOS	"
Lymphosarcoma, diffuse	"
Reticulum cell sarcoma, NOS	"
Reticulum cell sarcoma, diffuse	"
Reticulosarcoma, NOS	"
Reticulosarcoma, diffuse	"
Malignant lymphoma, small cleaved cell, diffuse	"
Malignant lymphoma, lymphocytic, poorly differentiated, diffuse	"
Malignant lymphoma, small cleaved cell, NOS	"
Malignant lymphoma, cleaved cell, NOS	"

Cancer Description	ICD-O-3 codes
Composite Hodgkin and non-Hodgkin lymphoma	M 9596/3

NOS = not otherwise specified.

Source: International Classification of Diseases for Oncology- Third Edition (ICD-O-3)

Note: All the cutaneous lymphomas listed in Table A4-3 will also be counted toward the "non-Hodgkin lymphoma" endpoint and toward the "Any lymphoma" endpoint but for simplicity purposes the diagnoses listed in Table A4-4 are limited to those that have not already been listed in Table A4-3.

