9.3.5 Endpoints

Incident malignancies are defined as the first occurrence of one of the malignancies of interest occurring in study patients during study follow-up. If a person develops more than one primary malignancy of interest (i.e., a malignant melanoma and a lymphoma), only the first malignancy will be included and counted as an individual record. In a sensitivity analysis, the occurrence of each endpoint will be evaluated regardless of a prior occurrence of any of the other study endpoints during the study period.

The third version of the International Classification of Diseases for Oncology (ICD-O-3), which provides site (topography) and histology (morphology) codes for neoplasms, will be used to define malignancies in the study. The ICD-O-3 topography code C44 (skin) will be used together with the corresponding morphology codes to identify malignant melanomas (MM) and non-melanoma skin cancers (NMSC). The complete lists of ICD-O-3 codes for the malignancies of interest are presented in Annex 4.

The following incident malignancies will be included in the study.

Skin Malignancies

- Malignant melanoma, including in situ carcinomas (MM)
- Non-melanoma skin cancer (NMSC), including in situ carcinomas (i.e., squamous cell and basal cell carcinomas, Merkel cell carcinoma, and adnexal and skin appendages neoplasms)

Skin malignancies will be evaluated as a group (“Any skin malignancy”) and by individual malignancy type—i.e., melanoma, NMSC. In a sensitivity analysis, NMSC will be further subclassified as basal cell carcinoma and squamous cell carcinoma.

Lymphomas

- Cutaneous T-cell lymphomas (CTCL)
- Hodgkin lymphomas (HL)
- Non-Hodgkin lymphomas (excluding CTCL)

Lymphomas will be analyzed as a group (“Any lymphoma”) and by specific lymphoma type—cutaneous T-cell lymphoma, Hodgkin lymphoma, and non-Hodgkin lymphoma (excluding CTCL). In a sensitivity analysis, lymphomas will be grouped as cutaneous or noncutaneous lymphomas.

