selected the ICD-O-3 codes that matched the definition and codes of cutaneous lymphomas in the WHO 2008 classification (see Annex 4, Table A4-3). This approach did not pose any problem for the identification of CTCLs. However, the identification of CBCLs (classified as a separate entity in WHO 2008) was not possible as the WHO 2008 codes for these tumors do not have correspondence in ICD-O-3. Therefore CBCLs (which occur considerably less frequently than CTCLs) will not be included within the cutaneous lymphomas group in this study although they are still expected to be identified as non-Hodgkin lymphomas in the study databases and would count toward that endpoint. Moreover, certain other rare lymphomas that were newly included with provisional codes in the WHO 2008 classification (and which are proposed for inclusion in the next edition of ICD-O), for example, primary cutaneous gamma-delta T-cell lymphoma, will not be explicitly included in this study. However, such lymphomas, if any occur in the study population and are coded less specifically, would be included in the non-Hodgkin lymphoma endpoint.

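### CTCL is defined by morphology codes with no skin-site requirement, so some lymphomas outside the skin can be counted as CTCL

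*Protocol*

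**What the plan says.** **Skin cancers.** Section 9.3.5 combines ICD-O-3 topography C44 with morphology codes to identify melanoma and non-melanoma skin cancer. Tables A4-1 and A4-2 repeat C44 in their titles.

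**CTCL.** Table A4-3 is headed "Morphology Codes for the Definition of Cutaneous Lymphomas With Primary Cutaneous Manifestations" and carries no topography code. It lists eight morphology codes: 9700, 9701, 9705, 9708, 9709, 9714, 9718 and 9719. Among them are "Anaplastic large cell lymphoma, T cell and Null cell type" (9714/3, which also covers the NOS form), "Primary cutaneous anaplastic large cell lymphoma" (under 9718/3), "NK/T-cell lymphoma, nasal and nasal type" (9719/3) and "Angioimmunoblastic T-cell lymphoma" (9705/3).

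**Rationale.** Section 9.3.5 says the codes were chosen by matching ICD-O-3 to the WHO 2008 cutaneous lymphomas, and adds: "This approach did not pose any problem for the identification of CTCLs". It treats primary cutaneous lymphomas as those that often appear first in the skin or commonly involve it fairly early. It contrasts them with lymphomas that reach the skin rarely or only when advanced.

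**Case checking (section 9.3.6).** Registry cases in Denmark and Sweden are not validated. In PHARMO a pathologist reviews every CTCL case. In the CPRD every CTCL case found through CPRD or HES records is reviewed. No skin-site criterion is given for either review.

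**The concern.** A registry case coded 9714/3 in a lymph node, or 9719/3 in the nose, with no skin lesion, meets the CTCL definition as written. Yet section 9.3.5 gives clinical distinctness from lymphomas that seldom involve skin as the reason for a separate cutaneous category.

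CTCL has the lowest incidence in Table 4 in both age groups (0.2 and 3.1 per 100,000 person-years), so a few misplaced cases can move the estimate. Section 9.9 says that results will be read from the point estimate, the upper confidence limit and the absolute excess risk. If the misplaced cases are less associated with exposure than true CTCL, the first two fall, and the result looks more reassuring than it should.

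The protopathic-bias review in section 9.3.6.1 is affected too. It asks whether CTCL symptoms were already present when treatment started, and that question has little meaning for a case without skin disease.

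**Working it through.** **1. Is there a site rule anywhere?**

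| Place | Site requirement for CTCL |
|---|---|
| 9.3.5, use of C44 | melanoma and NMSC only |
| Table A4-3 | none |
| 9.3.6, Denmark and Sweden | no validation of registry cases |
| 9.3.6, PHARMO | all CTCL reviewed, no site criterion |
| 9.3.6, CPRD | CTCL from CPRD or HES reviewed, no site criterion |
| 9.7.2.5, item 5 (cutaneous vs noncutaneous) | no separate definition; 9.3.5 points to Table A4-3 for the cutaneous codes |

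**2. Which codes can lie outside the skin, judged from the table alone?** For 9714/3 the evidence is direct: the primary cutaneous form has a separate code, 9718/3. For 9719/3 the name gives a nasal site. For 9705/3 the name gives no site, so it is not limited to skin, but the name does not show the contrary. That is three of eight codes, which is not a share of cases.

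**3. The plan's own CTCL figure.** Table 4 gives adults a probability of 0.33 and 0.85 that the upper 95% limit is below 2 and 4, at 3.1 per 100,000. With a = rate × person-years exposed cases, a true ratio of 1 and a 4:1 comparator, SE = √(1/a + 1/(4a)) and P = Φ(ln U/SE − 1.96).

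- Extension, 551,369 person-years: a = 551,369 × 3.1/100,000 = 17.1, SE = 0.270, P = 0.73 and 1.00.
- Phase I, 198,400 person-years: a = 198,400 × 3.1/100,000 = 6.15, SE = 0.451, P = 0.34 and 0.87.

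On the Extension person-years, Table 4 is not reproduced at 4:1, nor at 1:1 (0.53 and 0.98) or 2:1 (0.65 and 1.00). The Phase I person-years at 4:1 come within 2 percentage points. That is a separate matter. Here it shows only that expected exposed adult CTCL cases are few, at about 6 to 17.

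**4. Dilution (illustration only).** Let f be the share of comparator code-list cases that are non-cutaneous, R the true CTCL ratio and R₀ the ratio for non-cutaneous cases. Then

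observed ratio = (1 − f)R + f·R₀.

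The documents give neither f nor R₀. Assume R = 3, R₀ = 1, 68.4 comparator cases (4 × 17.1), 17.1 × observed ratio exposed cases, and log-Wald limits:

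| f | Observed ratio | Its upper limit | Upper limit, true CTCL cases only (ratio 3) |
|---|---|---|---|
| 10% | 2.8 | 4.05 | 4.39 |
| 20% | 2.6 | 3.79 | 4.50 |
| 30% | 2.4 | 3.53 | 4.62 |
| 40% | 2.2 | 3.28 | 4.79 |

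For f = 20%: exposed cases = 17.1 × 2.6 = 44.4, SE = √(1/44.4 + 1/68.4) = 0.193, upper limit = 2.6 × exp(1.96 × 0.193) = 3.79.

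The direction depends on R₀. At f = 20% and R = 3, R₀ = 1, 2, 3, 4 gives 2.6, 2.8, 3.0, 3.2. There is dilution only if R₀ is below R, and no bias if the two are equal.

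**5. Where would reassigned cases go?** Section 9.3.5 defines non-Hodgkin lymphoma as excluding CTCL. The note under Table A4-4 counts every Table A4-3 lymphoma toward non-Hodgkin lymphoma. The adult rates in Table 4 fit the exclusion: 18.1 + 4.4 + 3.1 = 25.6, the rate given for any lymphoma.

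**The case against.** The code list is deliberate. It follows a stated match to the WHO 2008 classification, and the working definition admits lymphomas that involve the skin fairly early, not only those that arise there. Whether each code belongs depends on WHO and ICD-O-3 sources that are not part of the protocol. A C44 filter could drop early-skin cases registered to another site. This explains why some codes are listed, but it does not make every case under them cutaneous.

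There are also safeguards. Every CTCL case is reviewed in PHARMO, as is every case from CPRD or HES records. The CPRD questionnaire may ask for the location and extent of CTCL and for biopsy results. Sweden plans a record review, pending ethics approval. These steps could reveal non-skin cases, but none states a site criterion or says that such a case leaves the endpoint, and none is planned in Denmark. The gap is narrowed, not closed.

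Three stronger readings are tempting and not supported:

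- **That a known, material dilution occurs.** The documents give neither f nor R₀.
- **That these cases are lost from the non-Hodgkin endpoint.** Section 9.3.5 implies this, but the note under Table A4-4 says the opposite. Any lymphoma is unaffected on either reading.
- **That CTCL alone carries the strongest earlier signal.** In section 7.1 the tacrolimus estimate of 3.1 (1.4–6.9) is for T-cell lymphomas, 80% of them cutaneous, so it is itself a mixed endpoint. The cutaneous-only tacrolimus estimate is 2.5 (0.5–12.6), and the Hodgkin point estimate is higher, at 5.3 (0.5–59).

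**Conclusion.** The concern holds as a defect of definition. CTCL has no skin-site requirement, at least 9714/3 and 9719/3 can be non-cutaneous on the table's own evidence, and 9705/3 is not limited to skin by its name. No step in sections 9.3.6 or 9.7.2.5 is stated to remove such cases.

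The consequence is conditional. If non-cutaneous cases are less associated with exposure than true CTCL, the rate ratio and its upper limit are biased toward 1. The 2.8 to 2.2 range for a true ratio of 3 rests on an assumed comparator share of 10% to 40% and an assumed ratio of 1 for those cases. It shows what the gap could do, not what it does.

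**What to change.** - **Definition.** In Table A4-3 and section 9.3.5, count 9714/3, 9719/3 and 9705/3 as CTCL only with topography C44, wherever ICD-O-3 topography is recorded (Denmark, Sweden, PHARMO through PALGA). Leave the other five codes as they are.
- **CPRD.** Apply the rule through the planned Read/OXMIS mapping to topography and morphology and through case review. State that registry cases coded in ICD-10 may not allow it.
- **Reporting.** Give CTCL results under both the site-restricted definition and the Phase I code list. Use the same site rule for the cutaneous versus noncutaneous sensitivity analysis.
- **Non-Hodgkin lymphoma.** Reconcile section 9.3.5 with the note under Table A4-4, so that reassigned cases have one defined endpoint.

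**Cost.** In the three ICD-O-3 sources this is an annex edit and a filter on a field already needed for the skin cancers. The CPRD needs more work. There will be fewer CTCL events: if 10% to 40% of counted cases were removed, the expected 17.1 exposed adult cases would become 15.4 to 10.3. The probability of an upper limit below 2 (true ratio 1, 4:1) would fall from 0.73 to between 0.68 and 0.51, or from 0.34 to between 0.31 and 0.22 on the Phase I person-years. Some early-skin cases registered to another site may be lost. The break with Phase I is covered by the parallel analysis.
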